11.6. Virology Analyses

The analyses will be performed on the FAS data set for whom virology endpoint measures are available.

Frequency and kinetics of clearance of HPV16 or HPV18 infection will be analyzed either combined or by HPV type (HPV16 or HPV18), and by infection type (persistent or recently diagnosed) using both the healthcare provider- and self-collected cervical samples and will be described for the vaccine regimens and placebo during the study duration.

11.7. Planned Analyses

A blinded interim analysis may be performed after all participants from Phase 1 of the study have completed the 21 days post-Dose 2 visit (Week 11) or have discontinued earlier. This analysis, which will include immunogenicity and safety data, will allow to identify immunogenicity and overall safety signals and guide further development of the vaccine.

The primary analysis will occur when all participants have completed the 6 months post-Dose 1 visit (Week 26) or have discontinued earlier. If enrollment is slow for HPV18-infected participants, an interim analysis may first be performed on the HPV16-infected participants. The primary analysis will then be performed on all participants when all HPV18 infected participants have completed the 6 months post-Dose 1 visit (Week 26) or have discontinued earlier. These analyses will include safety and virology data up to the 6 months post-dose 1 visit (Week 26) and immunogenicity data up to the 21 days post-Dose 2 visit (Week 11).

The final analysis will occur when the last participant completes the final visit at 12 months post-Dose 1 (Week 52, Day 366) or discontinued earlier to determine the durability of the immune response and analyze any additional safety, virology and immunological data collected after the primary analysis. If enrollment is slow for HPV18-infected participants, an interim analysis may first be performed on the HPV16-infected participants. The final analysis will then be performed on all participants when all HPV18 infected participants have completed the 12 months post-Dose 1 visit (Week 52) or have discontinued earlier.

The safety, virology and immunogenicity analysis will include the timepoints described in the **TIME AND EVENTS SCHEDULE**. At the time of the primary analysis, the study will be unblinded for sponsor personnel (including medical personnel, biomarker lead, virologist, statistician, programming and data management). Participants, clinical staff and study-site personnel will remain blinded to the study vaccine allocation until the end of the study.

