5. STUDY VACCINE ALLOCATION AND BLINDING

Study Vaccine Allocation

Randomization will be stratified by HPV type (16 and 18) and within each HPV type, randomization will be performed in different steps (see Table 1). Between the steps, randomization will be halted until a 24-hour and 7-day review by the PI and SRP or an IDMC review have been performed. For HPV16 infected participants the following randomization steps will take place:

- Step 1: 2 participants will be randomly assigned to receive low dose Ad26.HPV16 or placebo. These participants may be randomized on the same day.
- Step 2: 4 participants will be randomly assigned to receive low dose Ad26.HPV16 (3 participants) or placebo (1 participant). There will be a staggered interval of 7 days between the vaccination of each of these 4 participants.
- Step 3: 3 participants will be randomly assigned to receive high dose Ad26.HPV16 or the Ad26.HPV16/Ad26.HPV18 mix or placebo. These participants may be randomized on the same day.
- Step 4: 8 participants will be randomly assigned to receive high dose Ad26.HPV16 (3 participants) or the Ad26.HPV16/Ad26.HPV18 mix (3 participants) or placebo (2 participants). There will be a staggered interval of 7 days between the vaccination of each of these 8 participants.
- Step 5: 16 participants will be randomly assigned to receive high dose Ad26.HPV16 (6 participants), Ad26.HPV16/Ad26.HPV18 mix (6 participants) or placebo (4 participants). No more than 5 participants will be vaccinated per week.

The same randomization process will be used for the HPV18-infected participants.

If enrollment is slow for HPV18-infected participants, up to 8 HPV18-infected participants can be replaced by HPV16-infected participants, hence a minimum of 25 HPV18 participants will be allowed; the decision will be taken during Step 5.

Blinding

The participants, study-site personnel (including vaccine administrator) and investigator will be blinded to study vaccine allocation throughout the study, except for the pharmacist or qualified staff member with primary responsibility for study vaccine preparation and dispensing.

At the time of the primary analysis, the study will be unblinded for sponsor personnel (including medical personnel, biomarker lead, virologist, statistician, programming and data management). Participants, clinical staff and study-site personnel will remain blinded to the study vaccine allocation until the end of the study.

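### For slow HPV18 enrolment the primary and final analyses are triggered by HPV18 women alone, although up to 8 HPV16 replacements could then still be short of the visit

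*Protocol*

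**What the plan says.** Section 11.7 gives each analysis two triggers, and the Synopsis repeats them under Planned Analyses.

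- **General rule.** "The primary analysis will occur when all participants have completed the 6 months post-Dose 1 visit (Week 26) or have discontinued earlier". The final analysis follows when the last participant has completed the Week 52 visit or has discontinued.
- **Slow-enrolment rule.** "If enrollment is slow for HPV18-infected participants, an interim analysis may first be performed on the HPV16-infected participants". After that the primary analysis is to be "performed on all participants when all HPV18 infected participants have completed the 6 months post-Dose 1 visit". For the later milestone: "The final analysis will then be performed on all participants when all HPV18 infected participants have completed the 12 months post-Dose 1 visit". Both sentences allow for discontinuation. Neither asks for any HPV16 woman to have completed the visit.

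Section 5 attaches a second action to the same condition: "If enrollment is slow for HPV18-infected participants, up to 8 HPV18-infected participants can be replaced by HPV16-infected participants". At least 25 HPV18 women must remain, and the decision falls in Step 5, the last enrolment step. The footnotes to Tables 1 and 4 say the same.

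Section 11.7 also unblinds sponsor personnel at the primary analysis. That analysis is to cover safety and virology up to Week 26, and immunogenicity up to 21 days after Dose 2.

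**The concern.** The slow-enrolment sentences are safe only if HPV18 women are the last to reach the visit. The replacement rule, which applies under the same condition, can remove that premise: places that HPV18 women would have filled late in the study go to HPV16 women instead. If any of these is dosed after the last HPV18 woman, the two triggers point to different dates. The more specific one then starts an analysis of all participants while some are short of the visit.

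At the primary analysis, the Week 26 safety and virology data of these women would be incomplete, and sponsor personnel would be unblinded earlier than the general rule allows. At the final analysis, their Week 52 visit could be outstanding: the mandatory colposcopy, the provider-collected and self-collected samples, the durability blood samples and the last weeks of SAE follow-up. Section 11.7 plans no analysis after that one.

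**Working it through.** **How many women.** Tables 1 and 4 plan 33 HPV16 and 33 HPV18 women, 66 in all. The stated minimum reproduces: 33 − 8 = 25. Phase 1 takes 17 HPV18 women and Step 5 takes 16, so at the minimum 16 − 8 = 8 HPV18 women enter in Step 5 (17 + 8 = 25). HPV16 rises to 33 + 8 = 41. The most that can be affected is 8/66 = 12.1% of the study, or 8/41 = 19.5% of the HPV16 women.

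**How far short.** The documents give no enrolment rate, so the lag is an assumption.

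- Let the last HPV18 woman be dosed on calendar day 0 and attend on target. The triggers then fall 182 days later (Day 183) and 365 days later (Day 366).
- Let the 8 replacements start L days after her. Step 5 allows at most 5 vaccinations per week, so 5 are dosed at L and 3 at L + 7.
- Follow-up at the trigger is 182 − L and 182 − (L + 7) days for Week 26, and 365 − L and 365 − (L + 7) days for Week 52.
- Section 9.1.2 allows ±14 days at both visits, so the lower limits are 182 − 14 = 168 and 365 − 14 = 351 days.

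| Lag L (days) | Days of follow-up at Week 26 trigger (first 5 / last 3) | Days of follow-up at Week 52 trigger (first 5 / last 3) | Short of target | Below the window |
|---|---|---|---|---|
| 0 | 182 / 175 | 365 / 358 | 3 | 0 |
| 7 | 175 / 168 | 358 / 351 | 8 | 0 |
| 14 | 168 / 161 | 351 / 344 | 8 | 3 |
| 28 | 154 / 147 | 337 / 330 | 8 | 8 |
| 42 | 140 / 133 | 323 / 316 | 8 | 8 |

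A lag of 42 days is the length of the screening period. It would arise if a replacement entered screening on the day of the last HPV18 dose and used the whole period.

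**Role of the window.** For an individual replacement, a lag of up to 14 days is absorbed when the last HPV18 woman attends on target. If that woman attends 14 days early, the trigger falls at day 168 and no lag is absorbed. If she attends 14 days late, it falls at day 196 and a lag of 196 − 168 = 28 days is absorbed.

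**After the fix.** With visits on target, waiting for the last replacement moves the trigger by L + 7 days: 14 days for L = 7, 21 for L = 14, 35 for L = 28 and 49 for L = 42. No participant is then short.

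**The case against.** The strongest reply is that the opening sentence of each paragraph already covers the replacements, because they are participants. The slow-enrolment sentences can be read as a sequel: the HPV16 women are analysed first, the HPV18 women are still outstanding, and the full analysis follows once they arrive. On that reading, when HPV16 replacements finish last the sequel does not apply and the general rule does.

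Much of this stands. A reader might infer that no rule covers the replacements. The documents do not support that, since the general trigger does. What does not stand is that the sequel reading settles the matter. The HPV16-first analysis is optional, nothing says that it must include the replacements, and the sentence that names the slow-enrolment case is the more specific of the two.

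A second reply is that the harm at the primary analysis is small, and this holds for the lags tabulated. In the worst row the last batch is on Day 134 (133 + 1). Dose 2 is due by Day 57 + 7 = 64, and the visit 2 months after Dose 2 by Day 64 + 56 + 5 = 125. These women would therefore have both doses, all solicited and 28-day unsolicited AE collection, the immunogenicity sample at 21 days after Dose 2, and that virology visit. They would lack the Week 26 visit with its self-collected sample, and 182 − 133 = 49 days of SAE follow-up. The final analysis is meant to pick up data collected after the primary one. Sponsor unblinding with follow-up still running is also planned, so only the part before Week 26 is additional.

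**Conclusion.** The point holds as a conflict between two stated triggers. It bites only if at least one HPV16 replacement is dosed after the last HPV18 woman. The number affected is then anywhere up to 8 of 66, and only women lagging by about two weeks or more fall outside the visit window, given on-target attendance by the last HPV18 woman. The lags are assumed. No hypothesis is tested, so neither error rate nor power is involved. The effect is incomplete Week 26 safety and virology data, earlier sponsor unblinding for those women, and possibly missing Week 52 data at the final analysis.

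Two stronger conclusions might be inferred and are not supported.

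- *That replacements necessarily come after the last HPV18 woman.* The protocol says only that the decision is taken during Step 5 and that 25 is a minimum. The two HPV types may enrol independently, so replacements could be dosed while HPV18 women are still being recruited, with no shortfall.
- *That the Week 52 data would be lost.* Section 17.9.1 defines study completion by the last visit of the last participant. Section 5 in general ties full code disclosure to study completion and database closure. Section 17.11 allows analyses made after the study report to be reported separately. The data could miss the planned final analysis, but they would still be collected.

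The harm is modest, but the protocol itself fixes these triggers and the correction is small, so it should be made.

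**What to change.** In both slow-enrolment sentences, in Section 11.7 and in the Synopsis, replace the condition on HPV18 women with: *all participants (both HPV types, including HPV16 replacements) have completed the visit or have discontinued earlier*. Each then matches the general trigger of its paragraph. Keep the optional HPV16-first interim analysis. Sponsor unblinding needs no separate change, because it is tied to the primary analysis and moves with it.

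The cost is one phrase in each of two sentences, in two places. If replacements are used and finish last, the analyses wait for the last of them, a delay equal to her lag behind the last HPV18 woman. If they do not finish last, nothing changes.

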11.8. Independent Data Monitoring Committee

An IDMC will be established to monitor data on an ongoing basis to ensure the continuing safety of the participants enrolled in this study. It will consist of members independent of the sponsor,

including at least 1 medical expert in the relevant therapeutic area and at least 1 statistician. The PI and SRP will inform the IDMC of any AE of concern.

The IDMC will convene to discuss any situation that meets a study vaccination pausing or stopping rule as outlined in Section 11.9. The IDMC responsibilities, authorities and procedures will be documented in its charter. In addition, the IDMC will review the 7-day safety data post-Dose 1 among all participants in Phase 1; initially in those receiving the low dose of Ad26.HPV16 or Ad26 HPV18 vaccine and then among all those dosed with high dose vaccine (Ad26.HPV16 or Ad26.HPV18) or the mixed vaccine (Ad26.HPV16/Ad26.HPV18). Further randomization and vaccination of participants will be suspended until this IDMC review is completed. The IDMC will also review 7-day safety data post-Dose 2 (MVA.HPV16/18) among all participants in Phase 1. Safety data for review will include solicited and unsolicited AEs, SAEs, and laboratory assessments. After these reviews, the IDMC will make recommendations regarding the continuation of the study. The conclusion of the IDMC will be communicate to the investigators, the IEC/IRB and the national regulatory authorities as appropriate.

The IDMC will review unblinded data. Details on the intervals of the safety evaluations and on how the integrity of the study will be maintained when the blind is broken with an IDMC analysis will be provided in the IDMC charter. Safety data from the primary analysis will be shared with the IDMC.

11.9. Study Safety Rules

Study Pausing Rules

If a study vaccination is considered to raise significant safety concerns (and a specific set of pausing criteria have been met), further vaccination of participants will be paused. The concerned data will be reviewed by the IDMC, after which the IDMC will recommend whether the pause can be lifted or not, or whether other steps are needed.

The occurrence of any of the following events will lead to a pause in further study vaccination. This list is only applicable for concerned AEs that occur up to 28 days after each vaccination and to concerned SAEs throughout the study.

1. Death of a participant; OR
2. One or more participants experience a SAE or a Grade 4 (solicited or unsolicited) AE or a persistent (upon repeat testing) Grade 4 laboratory abnormality; OR
3. One or more participants experience a diagnostic level 1, 2 or 3 criterion for anaphylaxis⁴³ within 24 hours of vaccination; OR
4. Two or more participants experience a Grade 3 unsolicited AE of the same type (as per medical judgment of the sponsor); OR
5. Two or more participants experience a persistent (upon repeat testing) Grade 3 laboratory abnormality; OR

6. Two or more participants experience a Grade 3 solicited AE of the same type and persisting as Grade 3 for longer than 3 consecutive days^a.

For number 2 and number 5: to assess abnormal laboratory values, the test must be repeated at least once, within 48 hours of the site becoming aware of the abnormal value.

For number 4, number 5, and number 6: after each IDMC review of similar AEs, the Committee will indicate the conditions under which it requires further notification and review of the subsequent similar AEs.

To enable prompt response to a situation that could trigger pausing rules, the investigator should notify the sponsor's medical monitor or designee (AND fax or email SAE form to Global Medical Safety Operations, if applicable), immediately and no later than 24 hours after becoming aware of any related AE of Grade 3 or above (AND update the eCRF with relevant information on the same day the AE information is collected).

A thorough analysis of all Grade 3 cases will be carried out by the sponsor's medical monitor or designee, irrespective of whether the criteria for pausing the study are met.

Based on the pausing criteria, the sponsor's medical monitor or designee then decides whether a study pause is warranted. All sites will be notified immediately in case of a study pause. The sponsor's medical monitor or designee is responsible for the immediate notification of IDMC members and coordination of a IDMC meeting in case of a study pause.

Vaccinations for an individual participant may be suspended for safety concerns other than those described in the pausing criteria, at the discretion of the investigator if he/she feels the participant's safety may be threatened. The sponsor's medical monitor or designee or the investigator(s) (upon consultation with the sponsor's medical monitor or designee) may initiate IDMC review for any single event or combination of multiple events which, in their professional opinion, could jeopardize the safety of the participants or the reliability of the data.

Vaccinations for the study may be suspended for safety concerns other than those described above, or before pausing rules are met, if, in the judgment of the IDMC, participant safety may be threatened.

Resumption of vaccinations will start only upon sponsor receipt of the written recommendations by the IDMC. The clinical site(s) will be allowed to resume activities upon receipt of a written notification from the sponsor. The communications from the IDMC will be forwarded by the investigator to the IRB/IEC and by the sponsor to the relevant health authorities, according to local standards and regulations.

^a The day of occurrence of the AE is counted as Day 1.

Stopping Rules for Study Termination

If any of the conditions below (stopping rules) are met, further vaccination of subjects will be stopped and following consultation with the IDMC the study terminated except for the safety evaluations of already immunized participants specified in the protocol and any further safety evaluations recommended by the IDMC:

- Death of a participant, considered related to study vaccine or if the causal relationship to the study vaccine cannot be excluded; OR
- One or more participants experience diagnostic level 1 criterion for anaphylaxis⁴³ within 24 hours of vaccination, clearly not attributable to other causes than vaccination with study vaccine.
 - Level 1 definition of anaphylaxis:
 - ≥ 1 major (see below) dermatological AND
 - ≥ 1 major cardiovascular AND/OR ≥ 1 major respiratory criterion (see below)

Major criteria

Dermatologic or mucosal	
 • generalized urticaria (hives) or generalized erythema • angioedema*, localized or generalized • generalized pruritus with skin rash
Cardiovascular	
 • measured hypotension • clinical diagnosis of uncompensated shock, indicated by the combination of at least 3 of the following: 
 • tachycardia • capillary refill time >3 s • reduced central pulse volume • decreased level of consciousness or loss of consciousness
Respiratory	
 • bilateral wheeze (bronchospasm) • stridor • upper airway swelling (lip, tongue, throat, uvula, or larynx) • respiratory distress—2 or more of the following: 
 • tachypnoea • increased use of accessory respiratory muscles (sternocleidomastoid, intercostals, etc.) • recession • cyanosis • grunting

* Not hereditary angioedema.

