Participants will also be instructed on how to note daily in the diary symptoms for 7 days post-vaccination (day of vaccination and the subsequent 7 days) of the following events: fatigue, headache, nausea, myalgia, arthralgia, and chills.

Unsolicited Adverse Events

The investigator or study-site staff will document any reported unsolicited AEs and perform causality evaluations from the time of ICF signature through 28 days after the first vaccination, and from the time of the second vaccination until 28 days afterwards. SAEs will be collected from the time of ICF signature until the study end.

Laboratory Safety Assessments

Blood samples will be collected for safety laboratory assessments (hematology and biochemistry) as follows on all participants:

- At screening^a
- At 7 days post-Dose 1 and post-Dose 2

The following tests will be performed by a central laboratory:

- **Hematology Panel**

Hemoglobin

White blood cell count with differential

Platelet count

Prothrombin time^b

Activated partial thromboplastin time^b

^a Clinical laboratory tests will be collected on all participants screened for this study.

^b Parameters only measured at screening

- **Biochemistry Panel**

Sodium
Potassium
Creatinine
Blood urea nitrogen
Aspartate aminotransferase
Alanine aminotransferase

Review and Grading of Laboratory Data

The investigator must review the laboratory results, document this review, and record any clinically relevant changes occurring during the study in the AE section of the eCRF. Laboratory reports must be filed with the source documents.

Laboratory values will be initially evaluated by the investigator according to central laboratory criteria. Abnormal values outside the central laboratory range of normal will be graded according to the toxicity tables from the FDA Guidance document “Toxicity Grading Scale from Healthy Adult and Adolescent Volunteers Enrolled in Preventive Vaccine Clinical Trials” (see [Attachment 2](#)). Laboratory values within central laboratory normal limits will not be FDA graded and will be considered as normal.

Any clinically significant abnormal laboratory value occurring during the 28-day follow-up after each vaccination will be captured as an AE. For clinically significant abnormal laboratory values, the test must be repeated within a reasonable period of the site becoming aware of the abnormal value.

Additional Clinical Laboratory Assessments

Additional clinical laboratory assessments will be performed:

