12.1.3. Severity Criteria

All AEs and laboratory data reported as AEs will be coded for severity using the FDA toxicity grading tables (see [Attachment 2](#)). Note that laboratory values within laboratory normal ranges (even if within a toxicity grade range), or laboratory values outside normal ranges that are not clinically significant in the judgment of the investigator, should not be recorded as AEs. For AEs not identified in the grading table, the following guidelines will be applied:

- Mild (Grade 1): Awareness of symptoms that are easily tolerated, causing minimal discomfort and not interfering with everyday activities.
- Moderate (Grade 2): Sufficient discomfort is present to cause interference with normal activity.
- Severe (Grade 3): Extreme distress, causing significant impairment of functioning or incapacitation. Prevents normal everyday activities.
- Potentially life-threatening (Grade 4): Symptoms causing inability to perform basic self-care functions OR medical or operative intervention indicated to prevent permanent impairment, persistent disability.

The investigator should use clinical judgment in assessing the severity of events not directly experienced by the subject (eg, laboratory abnormalities).

The toxicity grading scale used for laboratory assessments is based on the FDA toxicity grading table (see [Attachment 22](#)), consistent with the assessment grading used throughout the protocol. If a laboratory value falls within the grading as specified in the FDA table, but also within the laboratory normal limits, the value is considered as normal. For hemoglobin, both the actual value and the change from reference will be graded.

The severity of solicited AEs will be graded in the diary by the subject based on the severity assessment provided in the diary and then verified by the investigator using the FDA toxicity grading table (see [Attachment 2](#)).

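### The pausing rules count Grade 3 and 4 events whatever their cause, but the 24-hour notification clause that serves them covers only related AEs

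*Protocol*

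**What the plan says.** Protocol Section 11.9 lists six events that pause vaccination. Rule 2 is met by one participant with an SAE, a Grade 4 AE or a repeat-confirmed Grade 4 laboratory value. Rule 4 reads "Two or more participants experience a Grade 3 unsolicited AE of the same type (as per medical judgment of the sponsor". Rule 5 reads "Two or more participants experience a persistent (upon repeat testing) Grade 3 laboratory abnormality". Rule 6 needs two participants with the same solicited AE at Grade 3 for more than three days in a row. None of these mentions causality. The counting window is set by "This list is only applicable for concerned AEs that occur up to 28 days after each vaccination"; SAEs count throughout the study.

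The notification clause follows in the same section. Its stated purpose is a prompt response when a pausing rule might be triggered. It has the investigator notify the sponsor's medical monitor "immediately and no later than 24 hours after becoming aware of any related AE of Grade 3 or above", with eCRF entry on the same day. The next sentence begins "A thorough analysis of all Grade 3 cases will be carried out by the" sponsor's monitor and sets no deadline.

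For laboratory data, Section 9.2.1 says "The following tests will be performed by a central laboratory" and "Any clinically significant abnormal laboratory value occurring during the 28-day follow-up after each vaccination will be captured as an AE". Section 12.1.3 adds that "laboratory values outside normal ranges that are not clinically significant in the judgment of the investigator, should not be recorded as AEs".

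**The concern.** The notification trigger is narrower than the rules it is meant to serve. A site that sees a non-serious Grade 3 unsolicited AE and judges it unrelated has no 24-hour duty to tell the sponsor, yet that event counts toward rule 4. A confirmed Grade 3 or 4 laboratory value that the investigator considers not clinically significant is not an AE at all, so it cannot be a related AE. Rules 2 and 5 still count it, and under rule 2 a single Grade 4 value is enough.

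This is a first-in-human, blinded, multicenter study. Rules 4 to 6 need two participants, who may be at different sites. If the first case is not sent promptly, the second may not be recognised as the one that meets the rule. At stake is how quickly a met rule is seen between scheduled reviews.

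**Working it through.** The plan gives no figure on this point, so the check sets the counting rules beside the reporting routes.

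**1. Which counted events have a timed route?**

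| Event | Counted by | Timed route to the sponsor |
|---|---|---|
| Death or any other SAE | Rules 1, 2 | Yes: Section 12.3.2, 24 hours, any causality |
| Related AE, Grade 3 or above | Rules 2, 4, 6 | Yes: Section 11.9 clause |
| Local solicited AE, Grade 3 or above | Rules 2, 6 | Yes: related by definition (Section 12.1.2), so inside the clause |
| Non-serious Grade 3 unsolicited AE judged unrelated | Rule 4 | None stated |
| Confirmed Grade 3 or 4 laboratory value recorded as an AE, judged unrelated | Rules 2, 5 | None stated |
| Confirmed Grade 3 or 4 laboratory value judged not clinically significant | Rules 2, 5 | None stated |
| Non-serious Grade 4 AE judged unrelated (mainly an emergency visit without admission, since admission makes it an SAE under Section 12.1.1) | Rule 2 | None stated |
| Prolonged Grade 3 systemic solicited AE judged unrelated | Rule 6 | None stated |

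**2. Is causality left out of the rules on purpose?** It appears so. The stopping rules in the same section do carry a causality condition, both for death and for anaphylaxis.

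**3. Who must count?** The sponsor. Section 11.9 has the medical monitor apply the criteria, and rule 4 leaves the matching of event types to the sponsor. Rule 5 does not ask for the same analyte, so a site with one case cannot tell whether the rule is met.

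**4. What do the other routes add?**
- Section 9.2.1: the PI and the sponsor's study responsible physician must halt vaccination when a rule is met, whatever the cause. No deadline for bringing cases together.
- Section 11.9: the monitor's analysis of Grade 3 cases. No deadline.
- Section 11.9: repeat laboratory test within 48 hours. This times the retest, not a report.
- Section 11.8: AEs of concern go to the IDMC. No deadline, and values not recorded as AEs are not reached.
- Section 17.5: eCRF entry as soon as possible. No fixed limit.

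**5. How far do the scheduled reviews reach (Sections 3.1 and 11.8)?**
- They use 7-day data, while AEs count for 28 days: 28 − 7 = 21 days, and 21/28 = 75% of the window lies beyond them. The Step 4 review does add all available data from Steps 1 and 2. Scheduled laboratory panels fall at day 7, so this share does not apply to them.
- The sentinel reviews in Steps 1 and 3 name AEs only. Laboratory results are named at the IDMC reviews that close Steps 2 and 4. From the first dose of the step these fall at about 3 × 7 + 7 = 28 days (4 participants) and 7 × 7 + 7 = 56 days (8 participants), with a visit window of ±2 days.
- The 7-day IDMC reviews are described for Phase 1. None is described for the 32 Phase 2a participants, although the IDMC charter, which is not shown, may set further reviews.

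These figures describe the backstop. They are not estimates of delay.

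**6. Illustration on assumed rates (not from the protocol).** Let p be the chance that a participant has a Grade 3 unsolicited AE of one type, and q the share of such events judged related. With 66 independent participants and r the event probability, P(2 or more) = 1 − (1 − r)^66 − 66r(1 − r)^65. Rule 4 uses r = p; what reaches the monitor through the clause uses r = pq.

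| p | Rule 4 met | Two or more notified, q = 0.5 | q = 0.25 |
|---|---|---|---|
| 2% | 0.381 | 0.141 | 0.043 |
| 3% | 0.593 | 0.261 | 0.088 |
| 5% | 0.848 | 0.494 | 0.200 |

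This shows only that the filter can hide a met rule from the 24-hour route. It says nothing about how long the rule would stay unseen.

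**The case against.** The best case for the present wording has four parts.

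- **The excluded group is small.** Section 12.1.2 sets a low bar for related: suspicion is enough. What falls outside is events that a blinded investigator believes are otherwise explained. This stands, and it limits the size of the problem. It does not help with laboratory values that never become AEs.
- **The duty to act is assigned.** Section 9.2.1 has the PI and the sponsor's physician halt vaccination when any rule is met, and Section 11.9 lets the monitor or investigators call an IDMC review for a single event. This also stands, but neither provision says when a site must report, and a halt depends on someone having both cases in view.
- **Judgment is built in.** Section 11.9 opens with significant safety concerns and later has the monitor decide whether a pause is warranted. A met rule is therefore not certain to end in a pause. That does not excuse late recognition, because the monitor cannot judge what has not been reported.
- **Laboratory transfer may be timed elsewhere.** The tests are central, and the Laboratory Manual, not shown here, may set a deadline. That is possible; the protocol itself states none.

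A reader might infer that unrelated deaths or SAEs could go unreported, that dose escalation could proceed past an unreviewed gate, or that the events are lost. The documents support none of these. SAEs go to the sponsor within 24 hours whatever the cause, the step reviews take place regardless of the clause, and AEs are still entered in the eCRF and Grade 3 cases analysed.

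**Conclusion.** The mismatch is in the text and should be corrected. It is a gap in promptness: between scheduled reviews, a met pausing rule may be recognised late because some of the events it counts have no timed route to the person who counts them. The firm part is non-serious Grade 3 unsolicited AEs judged unrelated, together with confirmed Grade 3 or 4 laboratory values judged unrelated or not clinically significant. The small remainder is non-serious Grade 4 AEs and prolonged Grade 3 systemic solicited AEs judged unrelated.

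Neither the length of any delay nor the number of extra vaccinations can be derived from the protocol. It would be tempting to read the 75%, 28 days or 56 days as the delay; they mark only where the scheduled reviews stop helping.

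The conclusion assumes that the missing causality condition in rules 2, 4, 5 and 6 is intended. If relatedness was meant, the rules themselves need correcting instead.

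**What to change.** Reword the notification clause in Section 11.9 so that 24-hour notice and same-day data entry apply to:

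1. any related AE of Grade 3 or above, with no time limit, as now;
2. any other AE of Grade 3 or above, whatever its judged cause, with onset up to 28 days after a vaccination;
3. any Grade 3 or 4 laboratory abnormality confirmed on the 48-hour repeat test, whether or not it is recorded as an AE.

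Item 1 should stay separate. A single 28-day limit on the whole clause would remove the notice now given for related Grade 3 or higher AEs that start later. Section 12.3.1 still records such AEs when they are ongoing at the next vaccination or lead to discontinuation of study vaccine.

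The cost is one clause and a few more expedited notifications. On the laboratory side they come from at most 66 × 2 = 132 scheduled post-dose panels, and only from those with a confirmed Grade 3 or 4 value.
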